6.9.1.2. Rescue Therapy

If required, Investigators may prescribe / recommend prescription of rescue therapy for participants experiencing unacceptable worsening of atopic dermatitis. Additionally, individuals with uncontrolled atopic dermatitis could be at risk for a secondary skin infection. These participants may be prescribed an antimicrobial therapy to treat the infection as detailed below. Rescue therapy use is allowed throughout the entire study. There is no limit on the number of times that topical rescue therapy can be prescribed, although Investigators and participants may wish to consider whether the study is suitable for them if repeated courses are required.

Rescue therapy, including antimicrobial rescue therapy, should be prescribed as detailed below, and any specific deviations should first be discussed with the Medical Monitor. Participants rescued by such topical therapy will continue to take IMP and use of rescue therapy will be documented in the participant eDiary ([Section 6.6.1 eDiary](#)). Of note, Investigators should make every attempt to conduct the following assessments immediately prior to administering any rescue therapy, by use of an unscheduled visit, if needed:

- EASI
- vIGA
- PP-NRS
- AEs
- Concomitant Medications

For non-sensitive body sites:

- Moderate potency (grade IV and V – [Appendix 14.2](#)) topical corticosteroids, twice daily for up to 7 days

For sensitive sites e.g., head and neck:

- Topical tacrolimus (0.1%), topical pimecrolimus (1%) or grade VII topical corticosteroid, twice daily for up to 7 days

If topical rescue therapy fails to control symptoms adequately, then the participant should be considered for alternative systemic therapy or phototherapy by the Investigator/their practitioner, at which point they will be classified as a treatment failure and IMP will be discontinued.

For possible skin infection:

- Topical:
 - Appropriate courses of topical antimicrobial therapies, such as fucidic acid cream (e.g., Fucidin), are acceptable for use for skin infections, as required
 - If requiring concomitant moderate potency steroid therapy, fucidic acid with betamethasone 0.1% (as the valerate ester), (e.g., Fucibet cream) twice daily for up to 7 days
- Oral:
 - Appropriate course(s) of oral antibiotic(s) may be prescribed as per clinical need

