- Number of days of treatment with TCS/TCI rescue therapy per participant in Weeks 1-4, 5-8, 9-12 and 13-16 and for Weeks 1-16.
- Proportion of participants requiring TCS/TCI rescue therapy in Weeks 1-4, 5-8, 9-12 and 13-16 and for Weeks 1-16.

The secondary safety endpoints for the study are:

- Adverse events and serious adverse events.
- Change from baseline in vital signs.
- Change from baseline in ECG parameters.
- Change from baseline in clinical laboratory parameters.
- Change from baseline in physical examination findings.
- Worst-case change from baseline with respect to potentially clinical important criteria for vital signs, QTcF and clinical laboratory parameters.
- Worst-case change from baseline with respect to values outside the normal ranges for clinical laboratory parameters.

Exploratory endpoints to evaluate the time to onset of clinical response are:

- Time to first achievement of EASI-50.
- Time to first achievement of sustained EASI-50.
- Time to first achievement of EASI-75,
- Time to first achievement of vIGA of 0 or 1 with a 2-point improvement from baseline.
- Time to first achievement of vIGA of 0 or 1.
- Time to first achievement of a ≥ 2 point in improvement in PP-NRS score, in participants with a score of ≥ 2 at baseline.
- Time in days to first sustained ≥ 2 point in improvement in PP-NRS score, in participants with a score of ≥ 2 at baseline.
- Time to first achievement of a ≥ 4 point in improvement in PP-NRS score, in participants with a score of ≥ 4 at baseline.
- Time in days to first sustained ≥ 4 point in improvement in PP-NRS score, in participants with a score of ≥ 4 at baseline.
- Time to first achievement of a ≥ 2 point in improvement in SD-NRS score, in participants with a score of ≥ 2 at baseline.
- Time in days to first sustained ≥ 2 point in improvement in SD-NRS score, in participants with a score of ≥ 2 at baseline.

Exploratory endpoints to evaluate the effect of early use of topical corticosteroid rescue therapy on Week 16 responder status are defined in the following subgroups: the subgroup of participants with no rescue use at any time before Week 16 will be compared to subgroups of participants with rescue therapy use within only the first 4, 8, 12 and 14 weeks of treatment and to participants with rescue therapy use within the 2 weeks and 4 weeks prior to the Week 16 visit. For these subgroups, the following endpoints will be summarized:

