5.3.2.3 Prohibited Concomitant Medications

The following medications are not allowed at any point during the study:

- Live (attenuated) vaccinations (a non-replicating / non-live vaccine when the first dose of IMP was not taken within a 7-day window of the administration of vaccine is allowed).

Type 1 prohibited medications are prohibited concomitant medications which may affect efficacy requiring the concomitant medication to be immediately discontinued where possible once the use is discovered. If the prohibited medication cannot be discontinued for any reason, then the IMP should be discontinued:

- Emollients containing additives including SLS.
- Topical Corticosteroids (TCS) or Topical Calcineurin Inhibitors (TCI) (unless considered a rescue therapy).
- Topical PDE-4 Inhibitors.
- Bleach baths.
- Tanning beds.
- Leukotriene Receptor Antagonists.
- Allergen Immunotherapy.

Type 2 prohibited medications are prohibited concomitant medications which may affect efficacy requiring IMP discontinuation:

- Phototherapy treatment
- Systemic treatments that may lead to clinical improvements in atopic dermatitis, e.g., oral or injectable corticosteroids, methotrexate, azathioprine, cyclosporine, mycophenolate mofetil, JAK-inhibitors, biologic therapy, and other systemic immunosuppressive therapy (note single dose intra-articular or intra-lesional corticosteroid therapy is permitted).

If a prohibited medication is found to have been used, this will be captured into the protocol deviations log.

Prohibited medications will be identified by the sponsor in a separate spreadsheet.

Any medications taken during the study and classified as type 1 prohibited medications in the spreadsheet will be considered as type 1 prohibited medications with exception for

1. Medications which stopped at least 14 days before Day 1
2. Medications which started strictly before screening and carried on throughout study to week 16
3. Medications which are emollients and started on or after screening, but before Day 1
4. Medications which are emollients and started before screening and stopped before Day 1

Any medications taken during the study and classified as type 2 prohibited medications in the spreadsheet will be considered as type 2 prohibited medications with exception for medications which stopped at least 14 days before Day 1.

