5.3.3.14 Rescue Therapy

Rescue therapy use is allowed throughout the entire study: selected topical corticosteroids and calcineurin inhibitors systemic antimicrobials and topical antibacterial may be prescribed. An unscheduled visit will be performed to collect skin assessments prior to administering any rescue therapy, if needed.

Rescue therapy use will be documented as concomitant medication once prescribed and in a daily symptom diary during the whole course. Each rescue therapy course will be recorded in concomitant medication CRF separately, resulting in a one record in a concomitant medication dataset for each course.

Any medications taken during the study and classified as TCS/TCl rescue therapy medications in the sponsor provided spreadsheet with total course duration no more than 8 days (adjusted for dosing

frequency – only days with planned medication usage are counted in course duration) will be considered as rescue therapy with exception for medications which stopped at least 14 days before Day 1 – these cannot be rescue therapy.

For the number of courses of TCS/TCI rescue therapy in Weeks 1-4, 5-8, 9-12, 13-16, course will only be counted at the start day of course. If the rescue therapy course starts in one period and continues to the next period it will be counted only in the first period where the start of the course belongs. The number of courses of rescue therapy will be also evaluated for the whole period of Weeks 1-16.

For the same periods, rescue therapy use will be evaluated. In case of rescue therapy course overlap with the period, the participant will be considered as those who used rescue therapy in this period.

The number of days requiring TCS/TCI rescue therapy in Weeks 1-8, 9-16, 1-16 will be calculated as:

Number of days requiring rescue therapy (days) = min(therapy stop date, the end of the period date) – max(therapy start date, the start of the period date) + 1

In case of multiple rescue therapy medications concurrently, the day still will be counted only once.

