9.4.2 Response Endpoints

The following endpoints will be analysed in the same manner as described below:

- Percentage of participants achieving EASI-50, EASI-75, EASI-90 at Weeks 4, 8, 12 and 16
- Percentage of participants achieving vIGA of 0 or 1 with a ≥ 2 -point improvement from baseline at Weeks 4, 8, 12 and 16
- Percentage of participants achieving vIGA of 0 or 1 at Weeks 4, 8, 12 and 16
- Percentage of participants achieving vIGA of 0 at Weeks 12 and 16
- Percentage of participants achieving BSA-50, BSA-75 at Weeks 4, 8, 12 and 16
- Percentage of participants achieving BSA reduction to 3% or less at Weeks 4, 8, 12 and 16
- Percentage of participants achieving SCORAD-35, SCORAD-50, SCORAD-75 at Weeks 4, 8, 12 and 16
- Percentage of participants achieving improvement of ≥ 4 points in DLQI score from baseline at Weeks 4, 8, 12 and 16
- Percentage of participants achieving improvement of ≥ 2 , ≥ 4 points in PP-NRS score from baseline at Weeks 4, 8, 12 and 16

- Percentage of participants achieving improvement of ≥ 2 points in SD-NRS score from baseline at Weeks 4, 8, 12 and 16
- Percentage of participants achieving improvement of ≥ 4 points in POEM score from baseline at Weeks 4, 8, 12 and 16
- Proportion of participants requiring TCS/TCI rescue therapy in periods Weeks 1-4, 5-8, 9-12, 13-16 and Weeks 1-16.

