9.5.1.4 Response Subgroup Exploratory Endpoints

For the primary and secondary responder endpoints relating to EASI, IGA and BSA, summaries will be provided comparing the number and percentage of participants in each treatment group who respond at Week 16 between the following subgroups:

- Participants with no rescue therapy use
- Participants with no rescue therapy use after the Week 4 visit
- Participants with no rescue therapy use after the Week 8 visit
- Participants with no rescue therapy use within 4 weeks of the Week 16 visit
- Participants with no rescue therapy use within 2 weeks of the Week 16 visit
- Participants with rescue therapy use within 4 weeks of the Week 16 visit
- Participants with rescue therapy use within 2 weeks of the Week 16 visit

The population summary measure of interest will be the proportion of responders in each subgroup in each treatment group.

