Version 2.0, Final 16-Jan-2023

EDP1815-207

Number	Title	Population	Data Point Set	Programming notes
14.2.26.1	Summary and Analysis of PP-NRS With a ≥ 4 Point Improvement from Baseline for Participants with a Score of ≥ 4 at Baseline - GLMM	FAS	EDPS1	
14.2.26.2	Summary and Analysis of PP-NRS With a ≥ 4 Point Improvement from Baseline for Participants with a Score of ≥ 4 at Baseline - GLMM	FAS	EDPS2	
14.2.26.3	Summary and Analysis of PP-NRS With a ≥ 4 Point Improvement from Baseline for Participants with a Score of ≥ 4 at Baseline - GLMM	FAS	EDPS6	
14.2.27.1	Summary of Absolute Change from Baseline in SD-NRS Score	FAS	EDPS1	
14.2.27.2	Analysis of Absolute Change from Baseline in SD-NRS Score - MMRM	FAS	EDPS1	
14.2.28	Summary and Analysis of SD-NRS With a ≥ 2 Point Improvement from Baseline for Participants with a Score of ≥ 2 at Baseline - GLMM	FAS	EDPS1	
14.2.29.1	Summary of Percentage Change from Baseline in POEM Score	FAS	EDPS1	
14.2.29.2	Analysis of Percentage Change from Baseline in POEM Score - MMRM	FAS	EDPS1	
14.2.30.1	Summary of Absolute Change from Baseline in POEM Score	FAS	EDPS1	
14.2.30.2	Analysis of Absolute Change from Baseline in POEM Score - MMRM	FAS	EDPS1	
14.2.31	Summary and Analysis of POEM With a ≥ 4 Point Improvement from Baseline for Participants with a Score of ≥ 4 at Baseline - GLMM	FAS	EDPS1	Include in TLR
14.2.32.1	Summary of Number of Courses of Rescue Therapy	FAS	EDPS7	
14.2.32.2	Analysis of Number of Courses of Rescue Therapy – Poisson Regression	FAS	EDPS7	
14.2.33.1	Summary of Days with Rescue Therapy	FAS	EDPS7	
14.2.33.2	Analysis of Days with Rescue Therapy – Poisson Regression	FAS	EDPS7	
14.2.34	Summary and Analysis of Requirement for Rescue Therapy - GLMM	FAS	EDPS7	
14.2.35	Summary of Time to First Achievement of EASI-50 Response	FAS	EDPS1	
14.2.36	Summary of Time to First Achievement of Sustained EASI-50 Response	FAS	EDPS1	
14.2.54	Summary of Time to First Achievement of EASI-75 Response	FAS	EDPS1	
14.2.37	Summary of Time to First Achievement of vIGA of 0 or 1 with a ≥ 2 Point Improvement from Baseline	FAS	EDPS1	
14.2.55	Summary of Time to First Achievement of vIGA of 0 or 1	FAS	EDPS1	

Number	Title	Population	Data Point Set	Programming notes
14.2.38	Summary of Time to First Achievement of PP-NRS Score with a ≥ 2 Point Improvement from Baseline for Participants with a Score of ≥ 2 at Baseline	FAS	EDPS1	

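### A TCS/TCI course of more than 8 planned-use days is not counted as rescue, so the rescue-requirement endpoint and the rescue-use subgroups record a participant with only such a course as a non-user

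*SAP*

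**What the plan says.** - **Rescue definition.** SAP 5.3.3.14 accepts a medication on the sponsor's TCS/TCI rescue list as rescue "with total course duration no more than 8 days". The length is adjusted for dosing frequency: "only days with planned medication usage are counted in course duration". Each course is a separate concomitant-medication record, and a course that overlaps a period counts as use in that period.
- **Protocol course length.** Protocol 6.9.1.2 describes moderate-potency "topical corticosteroids, twice daily for up to 7 days", gives the same maximum for the options at sensitive sites, and sets no limit on the number of courses.
- **TCS/TCI that is not rescue.** The type 1 prohibited list in SAP 5.3.2.3 includes "Topical Corticosteroids (TCS) or Topical Calcineurin Inhibitors (TCI) (unless considered a rescue therapy").
- **Binary endpoint.** SAP 9.4.2 lists "Proportion of participants requiring TCS/TCI rescue therapy in periods Weeks 1-4, 5-8, 9-12, 13-16 and Weeks 1-16". The output is Table 14.2.34, "Summary and Analysis of Requirement for Rescue Therapy - GLMM", on EDPS7.
- **Subgroups.** Under SAP 4.2, "the subgroup of participants with no rescue use at any time before Week 16 will be compared to subgroups" defined by when rescue was used. SAP 9.5.1.4 labels the reference group "Participants with no rescue therapy use", and SAP 9.5.1 assigns these summaries to EDPS7.
- **EDPS7.** SAP 7.1.2.7 applies treatment policy to every intercurrent event except study discontinuation.
- **Handling elsewhere.** SAP 9.4.3.1 excludes participants with CRF rescue courses over 8 days from the count analyses, as possible recording errors. EDPS1 (SAP 7.1.2.1) gives type 1 prohibited medication the same 28-day rule as rescue. The introduction to SAP 7.1.2 defines TCS/TCI rescue by prescription and CRF record, with no duration limit.

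**The concern.** The duration test decides whether a course counts as rescue at all. A course that fails it is not rescue, and in an EDPS7 analysis prohibited-medication use changes nothing. Where no further rule applies, a participant treated with a longer topical course looks the same as one who used nothing.

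This affects two outputs. The rescue-requirement endpoint is inferential: SAP 9.4.2.2 reports adjusted odds ratios, confidence intervals and p-values for each active group against pooled placebo. The subgroup summaries serve the exploratory objective on early rescue use and Week 16 response, which needs a no-rescue group that really had no rescue. The protocol version of the endpoint (Protocol 3.1.2) has no duration filter, and the SAP's table of changes from the protocol does not list the 8-day rule. The Cohort 4 addendum refers back to the main SAP for derivations, so the same flag applies there.

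**Working it through.** The plan states no rescue rate, so there is no planned figure to reproduce. The sample size rests on EASI-50 and is not touched by this point.

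**Step 1: apply the rule to example courses.** With daily planned use, length = stop day - start day + 1, and the course is rescue if the length is 8 or less.

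| Course | Planned days | Rescue under 5.3.3.14 | Count analyses (9.4.3.1) |
|---|---|---|---|
| Day 25-31 (Example 2 in SAP 7.1.2.1) | 7 | yes | included |
| Day 25-32 | 8 | yes | included |
| Day 25-33 | 9 | no | excluded |
| Day 60-80 | 21 | no | excluded |
| Day 25-31 and Day 60-73 | 7 and 14 | first yes, second no | excluded |

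The Day 25-33 participant, with no other course, is a non-user in every period of Table 14.2.34 and enters the no-rescue subgroup. The last participant is a user over Weeks 1-16 because of the short course, but a non-user in Weeks 9-12 (Days 57-84), where only the 14-day course falls. By the same logic, a course on Days 100-112 (13 planned days) does not keep its user out of the subgroup with no rescue in the 4 weeks before Week 16.

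**Step 2: look for a safeguard that reaches these outputs.** The exclusion in 9.4.3.1 sits under the count endpoints; 9.4.2 and 9.5.1.4 have no counterpart. The 28-day rule for type 1 medication belongs to EDPS1, not EDPS7. SAP 9.4 assigns response estimands to EDPS1 while the output list gives EDPS7 for Table 14.2.34. That conflict needs settling, but neither choice alters the 5.3.3.14 flag.

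**Step 3: illustrate the size.** All rates here are assumptions. Let true use be 40% on placebo and 30% on active, and let L be the share of users whose only courses exceed 8 planned days. Recorded use = true use x (1 - L). The odds ratio (OR) is active against placebo. Share of the placebo no-rescue group who are actual users = 0.40 x L / (1 - recorded placebo use).

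| L placebo | L active | Recorded placebo | Recorded active | OR | Users in placebo no-rescue group |
|---|---|---|---|---|---|
| 0 | 0 | 40% | 30% | 0.64 | 0% |
| 10% | 10% | 36% | 27% | 0.66 | 6% |
| 20% | 20% | 32% | 24% | 0.67 | 12% |
| 30% | 30% | 28% | 21% | 0.68 | 17% |
| 30% | 10% | 28% | 27% | 0.95 | 17% |
| 10% | 30% | 36% | 21% | 0.47 | 6% |

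For example, at 30% and 10%: OR = (0.27/0.73)/(0.28/0.72) = 0.370/0.389 = 0.95.

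**The case against.** The strongest case against is that few participants would be affected and little would change. Classification is by course and by planned-use days. Two successive 7-day records both count, and a 14-day course planned on alternate days has 7 planned days and counts. A long record may be an error, as SAP 9.4.3.1 itself suggests: SAP 7.3.1 imputes a stop date with only month and year to the month end, and one with only the year to 31 December. The subgroup tables are descriptive, and Protocol 11.4.5 intends Week 16 data there to be used without imputation. TCS/TCI use is listed, and prohibited use goes to the deviation log.

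This limits the reach of the point. A reader might infer that everyone with a long course is scored as not requiring rescue; that is true only where no course of 8 days or less falls in the same period or window. A reader might also infer that these are the worst-controlled participants, but nothing in the documents links one long record to worse disease. Nor are they necessarily recent steroid users at Week 16, which depends on when the course ran.

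The objection does not remove the misclassification. If a long record is suspect, treating it as proof of no use is still wrong, and it conflicts with excluding the same participant from the count analyses. Using Week 16 data as observed is intended; placing a treated participant in the untreated reference group is a separate matter.

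**Conclusion.** The point holds in a limited form. Following the SAP as written, a participant whose only TCS/TCI course in the relevant period or window exceeds 8 planned-use days is a non-user in the rescue-requirement endpoint and in the rescue-use subgroups. The SAP handles the same participant differently in the count analyses and, through type 1 status, in EDPS1.

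The size is unknown. On the assumed 40% and 30%, the odds ratio barely moves if long-course-only shares are equal across arms, and moves materially in either direction if they differ. A claim that most of a rescue benefit would be lost needs an assumed excess of long courses on placebo; the opposite imbalance would exaggerate the benefit.

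It would also go too far to say that the primary analysis is compromised. It is unaffected provided the sponsor's spreadsheet classes long courses as type 1 prohibited medication. The definitions point that way, but the SAP does not say that a drug on the rescue list becomes type 1 when its course is too long.

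**What to change.** 1. For the rescue-requirement endpoint and the rescue-use subgroups, define use as any course of a medication that the sponsor's spreadsheet classifies as TCS/TCI rescue and that overlaps the period on or after Day 1, whatever its duration. Keep the overlap rule of 5.3.3.14. Classify by medication, so that a long course is not lost if its record is listed as type 1.
2. Use the 8-day limit only to trigger a data query, including a check of imputed start and stop dates.
3. Add a sensitivity analysis that excludes participants with over-8-day records, as 9.4.3.1 does.
4. Reconcile SAP 5.3.3.14, 7.1.2 and 9.4.3.1, and state which category a listed course over 8 days takes in EDPS1 to EDPS6. Reconcile the protocol's 7-day course with the SAP's 8-day cut-off, and SAP 9.4 with the output list on the data point set for Table 14.2.34.

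The cost is a short SAP edit, one derived flag and a rerun of the affected tables and figures. No new data are needed, because each course is already on the concomitant-medication CRF. The small downside is that some records with wrong or imputed stop dates will count as use.

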5.3.4 Safety

5.3.4.1 Duration of Exposure

The duration of exposure will be calculated as

Duration of exposure (days) = Treatment stop date – Treatment start date + 1

5.3.4.2 Treatment-Emergent Adverse Events

An adverse event (AE) will be classified as ‘treatment-emergent’ if the onset date/time was on or after the start date/time of study treatment. Where dates or times are missing or partially missing, AEs will be assumed to be treatment-emergent, unless there is clear evidence (through comparison of partial dates/times, see [Section 7.3.1](#)) to suggest that the AE started prior to dosing.

AEs will be classified into the following study phases based on the onset date/time of the AE after any imputations:

- Pre-Treatment Phase: All AEs with onset date/time prior to the first dose of randomised study treatment
- Treatment Phase: All AEs with onset date/time at the time of or after the first dose of randomised study treatment (Day 1) up to and including the date of the last dose of treatment received.
- Follow-up Phase: All AEs with onset date after the date of the last dose of treatment received.

For participants who complete 16 weeks of dosing per protocol, the Treatment Phase will be from Day 1 to the Week 16 visit, and the Follow-up Phase will start after the Treatment Phase and last until their last day in the study. In all cases the day will be assumed to start at 00:00 hours and end at 23:59 hours. Adverse events occurring in both the Treatment Phase and Follow-up Phase are classified as treatment emergent.

The onset phase of all AEs will be included in the relevant data listings.

6 Sample Size

Cohorts 1-3

The sample size was calculated using the assumption that data from the placebo participants in the three cohorts can be pooled prior to comparison with the EDP1815 treatment groups. No adjustments for multiple testing have been made.

The primary efficacy endpoint is the achievement of EASI-50 at Week 16. The pooled placebo response rate is estimated to be approximately 25% and a doubling of this to 50% for EDP1815 would be considered as clinically meaningful.

Using a two-sided test at the 5% level of significance, 58 participants in each treatment group would give 80% power to detect a difference in one of the EDP1815 cohorts compared to the pooled placebo group. There would also be more than 90% power to compare the pooled EDP1815 group to the pooled placebo group.

Under the assumption of a 20% drop-out of participants prior to Week 16 this will require a total of at least 73 participants to be enrolled in each treatment group. In order to allow for the 3:1 randomisation in each cohort this has been adjusted to 75 participants per treatment group to give a total of 300 participants recruited. With 75 EDP1815 participants and 25 placebo participants in each of the three cohorts.

Cohort 4

Using the same assumptions relating to the placebo rate, clinically meaningful difference, significance level, and drop-out rate as above for Cohorts 1-3, approximately 70 participants are required in each of the EDP1815 8.0×10^{10} and Cohort 4 Matched Placebo groups to provide approximately 80% power in detecting a difference between EDP1815 and placebo in Cohort 4.

In order to allow 50% of the placebo control group to be concurrent controls and 50% to be historic matched controls from Cohorts 1-3, a 2:1 randomization will be used to enroll 70 EDP1815 8.0×10^{10} subjects and 35 placebo participants to Cohort 4.

If sensitivity analyses indicate that pooling of the Cohort 4 placebo group with the Cohort 1-3 matched placebo data is inappropriate, then the power of the comparison between the Cohort 4 EDP1815 and placebo groups is approximately 65% if only Cohort 4 placebo participants could be used in the treatment comparisons.

7 General Considerations

